## 9. STUDY SIZE

The study will enroll a minimum of 27 and a maximum of 35 subjects (see section 9.1 for details). At least 5 subjects will have a self-reported history of heart failure.

### 9.1 Study size justification

EMAT will be used to establish equivalence between the modified WCD and the AUDICOR device (see section 8 for details). Using the TOST, the sample size calculation is based on testing the following two-sided hypotheses:

*Null hypotheses:*  $H_0: |EMAT_{WCD} - EMAT_{AC}| \geq \delta$

*Alternative hypotheses:*  $H_A: |EMAT_{WCD} - EMAT_{AC}| < \delta$

where,  $|EMAT_{WCD} - EMAT_{AC}|$  is the absolute value of the mean of the differences in EMAT measured by the WCD and AUDICOR devices and  $\delta$  is the equivalence margin. The sample size for tests of equivalence of means of paired variables (paired T-test) is given by :

$$n = \left[ \sigma \frac{z_{1-\alpha/2} + z_{1-\beta/2}}{\delta - |EMAT_{WCD} - EMAT_{AC}|} \right]^2 \quad (1)$$

where,  $n$  is the sample size,  $\sigma$  is the standard deviation of the differences,  $\alpha$  is the significance level, and  $\beta$  is the probability of type II error (1-  $\beta$  is the power).

Internal testing on seven subjects provided the following summary statistics:

$ EMAT_{WCD} - EMAT_{AC} $	7.26
$\sigma$	8.36
90% CI-lower limit	-13.4
90% CI-upper limit	-1.13

Using an equivalence margin ( $\delta$ ) of 12-ms,  $\alpha = 0.05$ , and  $1 - \beta = 0.8$  the sample size using Eqn. 1 is 27. Although all enrolled subjects are expected to complete the study, the maximum enrollment is specified as 35 subjects to ensure a sample of 27 subjects who complete the study.

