## 8. EVALUATION OF RESULTS

Equivalence of the modified WCD device to the AUDICOR device will be established by comparing the full sample EMAT data during quiet sitting. EMAT was chosen to establish equivalence because previous studies have shown the utility of EMAT in predicting or identifying patients with left ventricular dysfunction . The two one-sided test (TOST)  will be used to test equivalence. Because measurements from the two devices (WCD and AUDICOR) are made on the same subject, a paired T-test will be used. The equivalence margin will be set at 12-ms, which is 10% of the 120-ms EMAT threshold previously used to identify patients with left ventricular dysfunction (K051450 and K070136). Using TOST, equivalence will be established at  $\alpha = 0.05$  significance level if a  $(1 - 2\alpha) * 100\%$  confidence interval for the average difference in EMAT (WCD-AUDICOR) is contained within the interval [-12, 12].

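### Section 9.1 halves beta although the planned difference is not zero, so 27 subjects give about 89% power under the Section 8 rule, not the stated 80%

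*Combined protocol and SAP*

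**What the plan says.** Section 8 (Evaluation of results) fixes the test. Equivalence is judged by two one-sided tests on within-subject differences, for which "a paired T-test will be used". "The equivalence margin will be set at 12-ms". Equivalence is declared at alpha = 0.05 if the (1 − 2α) interval, which is a 90% confidence interval, lies wholly inside ±12 ms. Each one-sided test is therefore run at 0.05.

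Section 9.1 (Study size justification) gives the sample size as n = [σ(z(1−α/2) + z(1−β/2)) / (δ − |difference|)]². It says that β "is the probability of type II error" and that 1 − β is the power. The inputs come from a small pilot: "Internal testing on seven subjects provided the following summary statistics", namely an absolute mean difference of 7.26 ms, an SD of 8.36 ms and a 90% interval from −13.4 to −1.13 ms. With δ = 12 ms, α = 0.05 and 1 − β = 0.8 the section concludes that "the sample size using Eqn. 1 is 27". The enrolment cap of 35 is there to secure 27 completers.

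**The concern.** A TOST succeeds only if both one-sided tests reject. If the true difference is zero, the two margins are equally far away, each test can fail, and it is reasonable to give each half of beta. This plan assumes a difference of 7.26 ms, well over half the margin. One margin is then close and the other far off, and in practice only the near test can fail. Halving beta in that setting sizes the study for more power than is stated.

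Power is a design property that readers and regulators will take from Section 9.1. As written, 27 completers looks like the minimum for 80% power, and any shortfall looks like a drop below that level. The minimum of 27 and the cap of 35 both rest on this figure. The consequence is a wrong statement about the design, not an underpowered study at the planned inputs.

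**Working it through.** **Inputs.** From Section 9.1: |difference| = 7.26 ms (negative in sign, as the pilot interval shows), σ = 8.36 ms, δ = 12 ms, α = 0.05, β = 0.20. From Section 8: paired t, 90% interval, so 0.05 per side. The distance to the near margin is 12 − 7.26 = 4.74 ms, and σ/4.74 = 1.7637.

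**Reproducing 27.** n = [1.7637 × (z_a + z_b)]², using z(0.975) = 1.960, z(0.95) = 1.645, z(0.90) = 1.282 and z(0.80) = 0.842:

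| Alpha term | Beta term | n | Rounded up |
|---|---|---|---|
| z(0.975), as printed | z(0.90), as printed | 32.7 | 33 |
| z(0.95) | z(0.90) | 26.6 | **27** |
| z(0.975) | z(0.80) | 24.4 | 25 |
| z(0.95) | z(0.80) | 19.2 | 20 |

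Of these four, only one-sided alpha with halved beta returns the stated 27. The printed equation does not. Correcting beta alone in the printed equation gives 25, so the two terms have to be put right together.

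**Where the type II error lies.** At n = 27 the standard error is 8.36/√27 = 1.609 ms.

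- Near margin: 4.74/1.609 = 2.9 standard errors.
- Far margin: (12 + 7.26)/1.609 = 19.26/1.609 = 12.0 standard errors.

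The chance of failing the far test is effectively zero. Beta therefore belongs wholly to the near test.

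**Power under the Section 8 rule.** The normal approximation at n = 27 is Φ(2.946 − 1.645) = Φ(1.301) = 0.903. The exact paired-t TOST, integrating over the sampling distribution of the SD, gives:

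| n | Power |
|---|---|
| 20 | 0.788 |
| 21 | 0.806 |
| 26 | 0.878 |
| 27 | **0.889** |
| 33 | 0.938 |
| 35 | 0.950 |

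The noncentral t agrees with these values, and a simulation of 400,000 trials at n = 27 gives 0.889. The type II error at 27 is thus about 11%, close to half the stated 20%, as expected when beta has been halved and only one tail matters.

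**Sensitivity at n = 27.** With the SD held at 8.36 ms, power is 0.78 at a true difference of 8 ms, 0.68 at 8.5 ms and 0.57 at 9 ms. With the difference held at 7.26 ms, power is 0.77 if the SD is 10 ms.

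**The case against.** Four points can be made for the plan.

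1. *Halving beta is a legitimate conservative bound.* It guarantees at least the target power whatever the true difference, and the section cites a textbook for the formula. This is fair as far as it goes: read as "at least 80%", the claim is met. But Section 9.1 presents 0.8 as the power and does not say it is a lower bound.

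2. *The route to 27 is not shown.* 27 is also the smallest n with at least 80% power for a t-based TOST at 0.025 per side (0.809; n = 26 gives 0.793). Halved beta is therefore the likely source of the number, not a proven one. The other route would match a 95% interval, whereas Section 8 specifies 90%, so it does not rescue the stated 80%.

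3. *Nothing in the conduct of the trial changes.* The study is larger than 80% power requires at the planned inputs, the type I error is unaffected, and enrolment up to 35 protects the 27. This stands, and it limits the weight of the point.

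4. *Quoting 89% suggests more certainty than seven subjects allow.* The pilot 90% interval reaches −13.4 ms, beyond the −12 ms margin, and power falls quickly if the difference or SD is larger than planned. This also stands. It is a reason to report the figure with its conditions and a range, not to leave an incorrect one.

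**Conclusion.** The concern holds. On the plan's own difference, SD, margin and decision rule, 27 completers give 88.9% power (90.3% by the normal approximation), not 80%, and 80% needs 21. The pairing of n = 27 with power 0.8 does not describe the test in Section 8. The result assumes normally distributed paired differences, with a true mean difference of 7.26 ms in absolute value and a true SD of 8.36 ms. The discrepancy is conservative and does not threaten the equivalence conclusion, but the study-size justification should be corrected because it cannot be reproduced as written.

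**What to change.** In Section 9.1:

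- Replace z(1−β/2) with z(1−β), or replace Eqn. 1 with a t-based TOST power calculation.
- In the same edit, replace z(1−α/2) with z(1−α), so that the equation matches the 90% interval in Section 8.
- Keep n = 27 and the cap of 35. State that 27 completers give about 89% power at the pilot difference and SD, and that 80% would need about 21.
- Add one line on sensitivity, for example power of 0.78 at a difference of 8 ms and 0.77 at an SD of 10 ms, and note that the inputs come from seven subjects.

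The cost is one equation and a few recomputed figures. Enrolment, procedures and the analysis are unchanged.

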## **10. RISKS AND BENEFITS**

Some subjects may experience minor discomfort and skin irritation due the adhesive electrodes of the AUDICOR system and the vest assembly of the WCD system. Alarms from the WCD device due to poor contact of its electrodes may startle the subjects during testing. There will be no risk of shock to the subject because the defibrillation capability of the WCD system will be disabled.

There are no direct benefits for the subjects participating in the study.

## **11. ADVERSE EVENTS**

Adverse events will be recorded on the Case Report Form only if the Investigator feels the event may be causally related to the AUDICOR or the WCD systems. The Investigator must assess the severity as indicated on the Case Report Form.

Serious adverse events include any event that is fatal or life threatening, requires or prolongs hospitalization, or is permanently disabling. The Investigator will assess whether the adverse event is anticipated or unexpected. An unexpected adverse event is any adverse event not identified by nature, severity or frequency prior to the investigation. Anticipated events include, but are not limited to:

- Skin rash or irritation is commonly associated with the use of adhesive electrodes and the garment assembly.
- WCD alarms may startle subjects due to poor electrode contact.

An unanticipated adverse device effect (UADE) is defined as “any serious adverse effect on health or safety or any life-threatening problem or death caused by, or associated with, a device, if that effect, problem, or death was not previously identified in nature, severity, or degree of incidence in the investigational plan or application (including a supplementary plan or application), or any other unanticipated serious problem associated with a device that relates to the rights, safety, or welfare of subjects” (21 CFR 812.3(s)). UADEs must be reported by the clinical investigator to ZOLL and the reviewing IRB, as described below:

- For device studies, the investigator is required to submit a report of a UADE to the sponsor and the reviewing IRB as soon as possible, but in no event later than 10 working days after the investigator first learns of the event (§ 812.150(a)(1)).
- ZOLL must immediately conduct an evaluation of a UADE and must report the results of the evaluation to the reviewing IRBs and investigator within 10 working days after first receiving notice of the effect (§§ 812.46(b), 812.150(b)(1)).

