After settling into the new position, the front therapy electrode will be tapped twice by the test administrator, the time after tapping will be noted as the start time, a manual recording will be performed by holding the response buttons for 3-seconds, and at the end of 10 minutes the front therapy electrode will be tapped and the time will be noted as the stop time. After all ADL maneuvers are complete, the study coordinator will remove the WCD device by disconnecting the electrode belt, unplugging the battery from the monitor, and removing the garment off the subject. After five minutes, the garment will be reapplied and then electrode belt and battery will be reconnected to the monitor. The subject will wear the device for 10 minutes while sitting quietly. The removal and reapplication times will be noted.

Following the removal and reapplication section, the subject will continue to wear the WCD until the total use of the device is 12 to 16 hours, with at least 6 hours of overnight wear. During the overnight wear the subject will be expected to sleep at the testing site. In addition, subjects will fill a diary (see Appendix A) to note their non-testing WCD activities before and after sleeping; any non-testing activity that causes the device to alarm; and any activity while sleeping that causes the WCD to alarm.

After the overnight wear, removal and reapplication of the WCD device will be repeated, following the procedure as described previously, and the subject will wear the device for 10 minutes while sitting quietly. At the end of the testing, recording from the WCD device will be terminated by removing the battery and the garment will be removed from the subject. Data from the WCD device will be downloaded to the ZOLL servers. In addition, at the end

---

of testing each subject, the WCD monitor will be cleaned, packed appropriately, and returned to ZOLL.

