### 6. DATA COLLECTION

ECG and heart sounds data recorded by the AUDICOR® AM devices during the testing will be transferred from the data storage cards to the sponsor provided computer. Study coordinators will perform a manual download to transfer each subject's baseline and all automatically recorded ECG data by the WCD to the ZOLL servers. The WCD device will also collect and store complete recordings of ECG data, heart sounds data, device performance data, and subject-device interaction data. These data will be stored in the WCD monitor's removable storage and will be extracted upon return of the device to ZOLL. Case report forms will be used to collect general demographic and medical history information from subjects enrolled in the study. In addition, the study coordinator will record the start and end times of each activity of daily living maneuver and the removal and reapplication times of the WCD device.

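### Section 11 does not require a case report form entry for an adverse event, even a serious one, that the investigator judges unrelated to the devices, so that judgement cannot be reviewed from study data

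*Combined protocol and SAP*

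**What the plan says.** Section 11 opens with the recording rule: "Adverse events will be recorded on the Case Report Form only if the Investigator feels the event may be causally related" to either of the two systems. It then defines seriousness by outcome alone: "Serious adverse events include any event that is fatal or life threatening, requires or prolongs hospitalization, or is permanently disabling". No recording or reporting rule is attached to that definition.

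The investigator also grades severity and judges expectedness: "The Investigator will assess whether the adverse event is anticipated or unexpected". The section gives no relatedness scale and no second review of relatedness.

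The only reporting route to the sponsor and the ethics board set out in Section 11 is for UADEs: "UADEs must be reported by the clinical investigator to ZOLL and the reviewing IRB". The definition of a UADE covers serious effects "caused by, or associated with, a device", and extends to "any other unanticipated serious problem associated with a device that relates to the rights, safety, or welfare of subjects".

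Section 6 describes the rest of the case report form: "Case report forms will be used to collect general demographic and medical history information from subjects enrolled in the study", plus start and stop times of the maneuvers and of device removal and reapplication. The subject diary (Section 5.5 and Appendix A) logs activities and alarms, including "any activity while sleeping that causes the WCD to alarm".

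**The concern.** Relatedness is normally a field completed after an event has been written down, so that someone else can later agree or disagree with it. Here it is the condition for writing the event down. A judgement that an event has nothing to do with either device leaves no form entry to re-examine.

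This matters most for serious events. Each subject wears the WCD for 12 to 16 hours, 6 or more of them overnight, and at least five subjects are to report a history of heart failure (Sections 4.2, 5.5 and 9). If a serious event occurred and was put down to underlying disease, the protocol would not require it to appear in the study data. Section 13 allows the results to go to regulators. A statement that no adverse events were recorded would then mean only that none was thought possibly device-related.

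**Working it through.** The plan states no adverse event rate, count or safety endpoint, so there is no figure to reproduce. The check is whether any section requires an entry for an event judged unrelated.

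| Place | What it captures | Covers a serious event judged unrelated? |
|---|---|---|
| Section 11, recording rule | Events possibly related to either system | No |
| Section 11, seriousness definition | A definition only, with no recording duty | No |
| Section 11, UADE reporting | Unanticipated serious effects or problems with a device link | No, if no link is seen |
| Section 6, case report form | Demographics, history, test times | No |
| Section 6, device storage | ECG, heart sounds, device performance and interaction data | Signals only, not an event log |
| Section 5.5 and Appendix A, diary | Activities and alarms | No |
| Section 7, analysis | Heart sound and sleep measures | No safety analysis planned |
| Section 13, investigator records | Deviations, amendments, correspondence | No event log |

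No row supplies the missing requirement.

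**Direction of the effect.** Let R and U be the numbers of truly related and truly unrelated events. Let m be the share of related events judged not even possibly related, and f the share of unrelated events judged possibly related.

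- Entries on the form = R(1 − m) + U·f
- All-cause events missing = (R + U) − [R(1 − m) + U·f] = R·m + U(1 − f)
- Related events missing = R·m

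The all-cause shortfall is above zero whenever any event is judged unrelated. The related shortfall is above zero only if m > 0 and a related event occurs. None of R, U, m or f is in the documents.

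**Illustration only, on assumed values.** Let p be the expected number of events of any cause per subject and q the overall share judged unrelated. Expected entries are N·p·(1 − q). With p = 5%:

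| N | All events, N·p | q = 0.25 | q = 0.50 | q = 0.75 |
|---|---|---|---|---|
| 27 | 1.35 | 1.01 | 0.68 | 0.34 |
| 35 | 1.75 | 1.31 | 0.88 | 0.44 |

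The recorded fraction is 1 − q whatever N and p are, so over this assumed range it runs from 25% to 75%. This shows direction and does not estimate the trial's shortfall.

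**The case against.** The strongest defence is proportionality. The Protocol Summary classes the study as non-significant risk and noninvasive. Defibrillation is disabled (Sections 2.1 and 10), and criterion 4.6 excludes anyone reporting breathlessness, fatigue, leg or foot swelling or chest pain. Limiting capture to possibly related events is a stated choice in that setting. This stands, and it sets the priority. It does not explain why a serious event should go unentered, and short exposure in few subjects also makes fuller recording cheap.

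A reader might also infer several stronger things that the documents do not support:

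- **That only events believed to be device-related are recorded.** The threshold is possible relatedness, which is lower. Doubtful cases, where later review matters most, should be entered.
- **That an unrelated event leaves no trace.** The rule concerns the case report form. Site source notes are not described either way, and device recordings and the diary exist.
- **That a planned safety count is biased low.** Sections 3, 7 and 8 plan no such count. For a listing of possibly related events, omitting unrelated ones is a definition. Related events are lost only by misattribution, and the documents say nothing of how often that would happen.
- **That the filter removes events from UADE evaluation.** UADE reporting is a separate duty, is not made conditional on a form entry, and reaches problems associated with a device as well as those caused by it. It does rest on the investigator seeing a device link, but that comes from its own definition.
- **That the upper confidence limit on an event rate after zero events in 27 or 35 subjects measures the defect.** That limit reflects sample size and would be the same if every event were recorded.

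**Conclusion.** The point holds in a narrow form. Section 11 makes possible relatedness the condition for a case report form entry, and no other section requires an entry for a serious event judged unrelated. The all-cause record is therefore incomplete by construction, and an unrelated judgement cannot be reviewed from study data. Related events are missing only if one is judged not even possibly related. Neither shortfall can be sized from the documents.

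The conclusion assumes that the form's adverse event page, which is not in the documents, follows Section 11 and does not ask for more. Priority is modest. The EMAT equivalence test in Section 8 uses none of these data and is unaffected.

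**What to change.** Replace the opening rule of Section 11 with one that requires a case report form entry, whatever the judged cause, for at least every serious adverse event and preferably every adverse event. The window should run from first device application (the first AUDICOR session) to final removal (after the second). Seriousness, severity and investigator-assessed relatedness should be separate fields. Section 7 should add two simple listings: all events, and device-related events. The UADE text can stay as it is.

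The cost is a revised passage, a relatedness field if the form lacks one, and ethics board approval of the change as Section 13 requires. Observation lasts about one day per subject in at most 35 subjects, so the downside is a few unrelated minor entries. Limiting the change to serious events would add fewer still.

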## **12. SUBJECT CONSENT AND CONFIDENTIALITY**

Each subject will be informed of the potential risks and benefits, the purpose of the investigation, and the investigational nature of the study prior to their enrollment. The subject must freely sign the IRB approved Informed Consent Form prior to the start of the study.

Each subject will receive a unique subject identification number. Although the patient's name and identity will be known to the investigators and to ZOLL, no HIPAA sensitive data will be stored except on consent forms. Authorized personnel from the IRB will have access to subject records as required.

---

Subject data will only be accessible by a unique subject identifier. The database will not contain subject names nor will the LifeVest network (a password protected and encrypted website).

### 13. ADMINISTRATIVE RESPONSIBILITIES

The protocol, informed consent document, and relevant supporting information must be submitted to the IRB for review and must be approved before the study is initiated. In addition, any subject recruitment materials must be approved by the IRB prior to being used. This study will be conducted in accordance with the ethical principles that have their origin in the Declaration of Helsinki and that are consistent with Good Clinical Practice and applicable regulatory requirements. The study must be conducted in accordance with the regulations of FDA as described in 21 CFR 50 and 56, applicable laws and the IRB requirements.

ZOLL, as sponsor of the investigation, has responsibility for the overall study administration, including providing necessary materials for conducting the study. The investigator will be responsible to assure IRB approval of the protocol.

The sponsor must submit any protocol change to the IRB for review and approval before implementation. A protocol change intended to eliminate an apparent immediate hazard to subjects may be implemented immediately provided the reviewing IRB is notified within 5 working days.

The investigator is responsible for following the study protocol and maintaining records of all protocol deviations, protocol amendments, and significant correspondence related to the study. The investigator is responsible for obtaining and maintaining the original Informed Consents and Case Report Forms. All Report Forms must be signed by the investigator or by investigator's designee.

It is the responsibility of the investigator to provide each subject with full and adequate verbal and written information using IRB approved informed consent document, including the objective and procedures of the study and possible risks involved before inclusion in the study. Informed consent must be obtained prior to performing any study-related procedures. A copy of the signed informed consent must be given to the study subject.

All written materials, data, and reports will be kept confidential; however, the results may be submitted to the FDA or other regulatory bodies as part of the evaluation of the device.

